## 4.2 Mixed-methods operational research

Throughout the project, mixed-methods operational research studies will be conducted in HFs and communities, as well as at district and national levels, to understand the contextual factors that facilitate or impede the implementation, uptake, or sustainability of digital health interventions such as ePOCT+ in PHC settings. Examples of such factors may include socioeconomic and ecological profiles of patients and communities, working conditions of the clinicians in the HFs, general management of HFs, among others.

### 4.2.1 Baseline health facility assessment

Prior to the intervention, a baseline HF assessment will be conducted in all facilities chosen for the study to assess their basic readiness to provide health services, with an emphasis on child health. The questionnaire used in this survey is an abbreviated version of the Service Provision Assessment (SPA) inventory tool used nationally, complemented with additional questions that relate specifically to the implementation of digital health interventions. The survey will be repeated annually in all HFs regardless of where they are in the implementation process to ensure that no major changes in the general operation of the facilities have occurred that could bias the results of the study. The modified tool used in the study can be found in **Appendix B** (B1).

### 4.2.2 Cross-sectional quality of care survey

Cross-sectional surveys will be conducted to assess changes in the quality of care over time, from the baseline through the implementation of ePOCT+. Two main rounds of the survey will be conducted spaced approximately 20 months apart: prior to the intervention and during Phase 2. To account for the sequential start of the three parallel cluster studies, three additional smaller rounds of the survey will be conducted to constitute a third full round of the survey and to systematically compare quality of care between intervention and control facilities. Timing of the cross-sectional survey is marked by "x" in **Figure 6**. The surveys will be conducted in a subset (n=18) of randomly selected HFs to assess the quality of the consultation done by HWs and their level of compliance to the algorithm (and thus to guidelines). Clinical research assistants will attend and observe (without interfering) 25 consecutive consultations with children enrolled into the study per HF, thus a total of 450 HW/child pairs per round. Concurrently, client exit surveys will be conducted at the end of the consultation (linked to the observation data) to evaluate the caregiver's perception of the health care the child received. The questionnaire for this survey is adapted from the Service Provision Assessment (SPA) sick child client exit interviews (USAID et al. The Demographic and Health Surveys Program), a methodology recommended by the WHO. The modified tools used in the study can be found in **Appendix B** (B2, B3).

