### 8.1.4 Training of health workers

Following the study design, training of HWs will be rolled out in a sequential manner. Each implementation block includes facilities that will receive the intervention right away (e.g. group 1) and facilities that will start with a 4-month control period (e.g. group 2) that require different training approaches.

Before the start of the control period (applicable to groups 2, 4 and 6): All skilled HWs who are engaged in triage, assessment, and clinical management of sick children will receive training in study-

related procedures, including consent for electronic recording of data and documentation of the final decision on referral, tests performed, final diagnoses and treatments using the tablet. Additionally, the research team will ensure that the standard paper guidelines (IMCI and Rwandan national treatment guidelines) are available in all HFs and HWs will be reminded that these guidelines should be followed during patient management.

Before the start of Phase 1 (applicable to all groups except group 6): HWs will receive training on how to use the ePOCT+ application on the tablet, using clinical case studies, as well as job aids for conducting and interpreting the results of POC tests which are not currently part of standard care at PHC level but are included in the algorithm (e.g. pulse oximetry and CRP rapid test). HWs will also be trained on the epidemiology of diseases in Rwanda, the most important pediatric diseases and their clinical predictors, and the importance of rational antibiotic and antimalarial use. They will also be able to review the content of the ePOCT+ algorithm and practice key clinical skills via the use of the e-learning tool. Additionally, training will be provided on the use of the medAL-monitor/medAL-outbreak tool (see Section 8.1.5).

During the month following this centralized training, HWs in control facilities will benefit from one and in intervention facilities from two visits from the implementation team for in-service face-to-face training during which trainers will accompany them in some of their consultations with real patients and help them optimize the way they use ePOCT+. Trainers will also support reorganization of workflows in the HF if necessary.

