## 9.4 Analyses of data from mixed-methods studies

Quantitative data from cross-sectional quality of care surveys, provider clinical competency or knowledge assessments, and caregiver and patient interviews will be analyzed using conventional statistical methods to compare means (t-tests or paired t-tests) or frequencies (chi-square tests) across intervention groups or time periods. Regression analysis may also be used to explore associations of multiple predictors with outcomes of interest.

Qualitative interviews and focus group discussions will be audio-recorded and detailed notes will be taken. Records will be manually transcribed in their original language and translated into English. A qualitative data analysis software (e.g. Dedoose, Nvivo, ATLAS.ti) will be used to code the English interview transcripts in order to identify emerging themes. A predefined list of codes based on the interview guide and the recurrent themes highlighted in the detailed notes will be used. New codes will be created when new themes are identified during more detailed analysis of the transcripts. Deductive coding will be used to extract the themes based on the interview guide, but inductive coding will also be used to extract any unexpected themes that arise during the interviews.

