#### *The project overall:*

The project provides many benefits, as described above, but also comes with some risks. For example, clinicians may be hesitant to use the tool, because it is difficult to use or they feel it is too prescriptive, etc. As CDSAs cannot cover all possible clinical situations, even in a well-defined patient target group, HWs are ultimately responsible for the clinical management of all patients and may override the recommendations of the algorithm and provide additional or withhold treatment according to their own clinical judgement. To mitigate this, qualitative research will be conducted to solicit user feedback and facilitate improvements to ensure that the ePOCT+ application meets user needs. Furthermore, the application may be perceived by some stakeholders as a “black box” and be wary of the use of machine learning for algorithm adaptation, which may reduce their trust in the system. To ensure full transparency, as requested more and more by stakeholders (Ansermino et al. 2019), the medical content of the algorithm used during Phase 1, as well as any modification introduced during Phase 2, even if applied only in some geographical areas or for a short period of time, will be published in real-time on the website dedicated to the DYNAMIC study. Health authorities and HWs will thus always have access to this content and know the exact combinations of clinical predictors used to suspect or diagnose each disease. No change in the algorithm will take place automatically and all modifications will be introduced manually. ML will be used only in the background, to complement conventional statistical methods to analyze data and guide decisions of the clinical expert group. For safety reasons, ML will never be used within the algorithm. Lastly, in Phase 2 of the study, when the intervention is introduced in all or nearly all HFs in the intervention area, there will be no control group. There is a possibility that due to circumstances that are external to the project (e.g. severe weather events, food insecurity, disease outbreaks) childhood morbidity and mortality could increase. In order not to incorrectly attribute poor outcomes to the study, we will need to monitor these events as closely as possible.

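### The main quality-of-care rounds compare before with after and have no control, and the plan does not commit to using the baseline round in the between-arm comparison that could test Hypothesis 2

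*Protocol*

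**What the plan says.** - **Purpose and timing.** Protocol 4.2.2: "Cross-sectional surveys will be conducted to assess changes in the quality of care over time, from the baseline through the implementation of ePOCT", with "Two main rounds of the survey will be conducted spaced approximately 20 months apart: prior to the intervention and during Phase 2".
- **Between-arm round.** The same section adds three smaller rounds, which together make a third full round, to "systematically compare quality of care between intervention and control facilities". The synopsis (Procedures and measurements) also lists the survey as a data source for comparing the arms.
- **Size.** "The surveys will be conducted in a subset (n=18) of randomly selected HFs", observing "25 consecutive consultations with children enrolled into the study per HF, thus a total of 450 HW/child pairs per round". The section does not say whether the same 18 facilities are visited each time.
- **Phase 2.** The synopsis has all facilities on ePOCT+ in Phase 2. Protocol 11.2 says that then "there will be no control group".
- **Allocation.** The synopsis and SAP 3.2 say that facilities are split into arms geographically and not at random. One sentence in SAP 3.1 speaks of randomised clusters. I follow 3.2 and the synopsis.
- **Analysis.** Protocol 9.4 plans conventional methods "to compare means (t-tests or paired t-tests) or frequencies (chi-square tests) across intervention groups or time periods". Its next sentence permits regression for exploration. The SAP does not cover this survey.
- **Claim at stake.** Hypothesis 2 (Protocol 2.1) is causal: quality of care is expected to improve because ePOCT+ is used.

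**The concern.** The survey can yield two contrasts, and each lacks something. The baseline-to-Phase 2 contrast has no control trend, so any change that all facilities share is mixed with the effect of ePOCT+. One source of such change is visible in the plan: rounds 20 months apart sit 20 − 12 = 8 months apart in the calendar year, and Protocol 5.1 describes a May to September dry period. For antibiotic prescription, SAP 6.2 uses the control arm to correct for seasonality. No equivalent is stated for quality of care.

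The third-round arm contrast has a concurrent control, so shared change does not bias it. Its weakness is that geographically separated arms may have differed in quality before the trial. The baseline characteristics in SAP 5.4 include patient volume, a service readiness score, age, sex and reasons for attending, but not observed consultation quality. The pre-intervention survey round is the direct measure of that difference, and no section commits to using it in the arm contrast.

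**Working it through.** **1. The plan's own figure.** 18 facilities × 25 consultations = 450 per round, as stated.

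**2. What each contrast estimates.** Let *b* be the arm gap before the trial, *s* the change common to both arms and *t* the true effect.

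- Baseline to Phase 2: *s + t*
- Third round, intervention minus control: *b + t*
- Difference in change, (intervention third round − baseline) − (control third round − baseline): *t*, provided that nothing else changed differently between the arms

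| *b*, *s*, *t* (points) | Before-after | Arm contrast | Difference in change |
|---|---|---|---|
| 5, 10, 0 | 10 | 5 | 0 |
| 5, 10, 10 | 20 | 15 | 10 |

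**3. Illustration with the simple tests of 9.4.** Assume an item done in 50% of consultations, *t* = 0, and observations treated as independent.

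- Shared change of 5 points, 450 v 450: SE = √[(0.25 + 0.2475)/450] = 3.3 points. 5/3.3 = 1.50, and the chance of a significant result is about 32%. At 10 points it is about 86%.
- Prior gap of 5 points, 225 v 225 (assuming 9 facilities per arm): SE = √[(0.25 + 0.2475)/225] = 4.7 points, and the chance is about 18%. At 10 points it is about 57%.

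The sizes of *s* and *b* are assumed. These rates show how the tests respond, not how likely such changes are.

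**4. Gap from facility variation alone.** SD of the arm gap = √(2 × ICC × 0.25/9). This is 3.7 points at ICC 0.025 and 7.5 points at ICC 0.10, before any systematic geographical difference. The documents give an ICC of 0.025 for prescribing and none for the survey.

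**5. What baseline adjustment achieves.** Let *c* be the between-round correlation of facility effects, assumed 0.5 to 0.8. With equal variances in the two rounds, the facility-level correlation is *r* = *c* × ICC/[ICC + (1 − ICC)/25]. The adjusted contrast leaves a share 1 − *r* of a persistent gap. Its variance relative to the unadjusted contrast is (1 − *r*²)(1 + 1/14), without block terms.

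| ICC | *c* | *r* | Gap left | Variance ratio |
|---|---|---|---|---|
| 0.025 | 0.5 | 0.20 | 80% | 1.03 |
| 0.025 | 0.8 | 0.31 | 69% | 0.97 |
| 0.05 | 0.5 | 0.28 | 72% | 0.99 |
| 0.20 | 0.8 | 0.69 | 31% | 0.56 |

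Adjustment therefore removes only part of a persistent gap, and at ICC 0.025 it barely changes precision.

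**6. What the difference in change costs.** With 9 facilities per arm, SE = √{4[ICC × 0.25 × (1 − *c*) + (1 − ICC) × 0.25/25]/9}. The unadjusted third-round SE is √{2[ICC × 0.25 + (1 − ICC) × 0.25/25]/9}. For *c* from 0.5 to 1.0:

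- ICC 0.025: 6.6 to 7.6 points, against 6.0 unadjusted
- ICC 0.10: 6.3 to 9.8 points, against 8.7 unadjusted

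It removes the gap in full, but is less precise when *r* is below one half.

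**The case against.** The strongest reply is that the protocol already plans the right comparison. Section 4.2.2 describes change over time and adds a full round to compare the arms, and no sentence says that Hypothesis 2 will be judged on the baseline-to-Phase 2 change. This stands. A reader might infer that the plan credits the whole before-after change to ePOCT+. The documents do not say so. That reading only joins the survey's stated purpose to Hypothesis 2.

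Section 9.4 is also a generic sentence covering several studies, and its optional regression could include the baseline value. The baseline round is therefore uncommitted, which is weaker than excluded.

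A reader might also cite Protocol 8.1.4, where "HWs will be reminded that these guidelines should be followed during patient management", as a change that lifts both arms. That paragraph concerns groups 2, 4 and 6 before their control period. Guidelines are to be available in all facilities, but no matching reminder is stated for groups 1, 3 and 5. A reminder given to controls only would be a differential change in Phase 1, which neither baseline adjustment nor the difference in change removes.

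The annual facility assessment (4.2.1) and the monitoring of external events (11.2) are real safeguards, and 11.2 openly acknowledges the missing control. Neither is a statistical adjustment for consultation quality.

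Finally, the survey is one part of the operational research.

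**Conclusion.** The point holds in limited form. The baseline and Phase 2 rounds have no concurrent control and cannot by themselves support a causal claim about quality of care. The planned between-arm round can address it, but the stated tests do not commit to accounting for prior quality differences between geographically allocated arms, although the survey that measures them is already planned.

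The size of any bias cannot be read from the documents. It equals *s* for the before-after contrast and *b* for the arm contrast, and both are unknown. The 5- and 10-point values, the 50% level, the 9 v 9 split, ICCs other than 0.025 and the between-round correlations are assumptions. Baseline adjustment is an improvement and not a cure: it leaves about 31% to 72% of a persistent gap at ICC 0.05 to 0.20, and 69% to 80% at 0.025. The change is worth making because it is cheap. The primary outcome is unaffected.

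**What to change.** In Protocol 4.2.2, state that the same 18 facilities are surveyed in every round.

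In Protocol 9.4:

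1. Test Hypothesis 2 by the facility-level contrast between arms in the block-timed third round, accounting for implementation block and adjusting for the same facility's pre-intervention value.
2. Report the difference in change from baseline as a sensitivity analysis, because covariate adjustment removes a persistent gap only partly.
3. Report the baseline-to-Phase 2 change descriptively, not as an effect of ePOCT+.

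**Cost.** Wording only, with no new data if the facilities are revisited. With three blocks, the model fits an intercept, arm, two block terms and the baseline value, leaving 18 − 5 = 13 residual degrees of freedom against 16 for a plain two-group comparison. Precision gains little or nothing if the ICC is near 0.025 (variance ratio about 0.97 to 1.03), and the difference in change is less precise in some scenarios. The before-after change can no longer be presented as an effect.

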Statistical considerations	
For the parallel cluster study in Phase 1, the primary analysis will evaluate whether the use of ePOCT+ for case management of sick children in PHC facilities results in decreased antibiotic prescriptions (superiority analysis) at the initial consultation. Superiority in antibiotic prescription is defined as a relative decrease of <math>\geq 25\%</math> in the proportion of children prescribed an antibiotic. We estimated a cluster size of 660 patients (monthly utilization of 220 – accounting for up to 30% non-adherence from 315 – over 3 months) and an intraclass correlation coefficient of 0.025. To have 80% power to detect a 25% reduction in antibiotic prescription (e.g. from 35% to 26%), for a one-sided hypothesis test at alpha of 0.025, we would require a minimum of 11 clusters per arm. With 16 clusters (or HFs) per arm, over 3 months, we expect a total of 10,500 participants per arm, this sample size is sufficient to test for non-inferiority in the secondary outcome (clinical cure at day 7) between the control and intervention groups.
 
We will test for significant difference in the primary outcome of antibiotic prescription between study arms by comparing proportions and their 95% confidence intervals. Primary analysis of superiority will be performed according to the intention-to-treat principle. The results will be stratified by sex, age group (young infants ages 1 to 59 days, children aged 2 months to 5 years, and children aged 5 to 14 years), and select clinical variables (respiratory symptoms, fever without clinical source, gastrointestinal complaints, skin problems, ear and throat problems, anemia, and malnutrition).
 
At the estimated utilization of the PHC facilities in Nyamasheke and Rusizi districts, we anticipate that approximately 150,000 consultations will be conducted using ePOCT+ throughout the study.

Study duration and schedule	
Pilot phase: April 2021 – August 2021
 
Phase 1 (data collection): September 2021 – April 2022
 
Phase 2 (data collection): June 2022 – December 2022
 
Implementation research (data collection): October 2020 – October 2022
 
Sustainability assessment: August 2022 – December 2022

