A separate consent process will be used for the participants of the mixed-methods operational research studies. For example, as part of the cross-sectional quality of care surveys, trained research clinical observers will ask HWs present on the day of data collection for permission to observe a series of consultations. They will then ask the HW to request oral permission from their patient and to sign a consent form indicating their own and the patient's consent to have an observer in the room. The caregiver will also give consent to be subsequently interviewed by a different research assistant upon the completion of their consultation. Similarly, the participants of qualitative interviews or FGDs, or quantitative surveys will be recruited and asked for their consent to participate. The Informed Consent Forms associated with the study can be found in **Appendix C**.

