## 9 STATISTICAL METHODS

### 9.1 Sample size calculations

For the parallel cluster study in Phase 1, the primary analysis will evaluate whether the use of ePOCT+ for case management of sick children in PHC facilities results in decreased antibiotic prescriptions (superiority analysis) at the initial consultation. Superiority in antibiotic prescription is defined as a relative decrease of  $\geq 25\%$  in the proportion of children prescribed an antibiotic. We estimated a cluster size of 660 patients (monthly utilization of 220 – accounting for up to 30% non-adherence from 315 – over 3 months) and an intraclass correlation coefficient of 0.025. Non-adherence here is defined as HWs not using the application for all eligible patients that come to the HF for various reasons. To have 80% power to detect a 25% reduction in antibiotic prescription (e.g. from 35% to 26%), for a one-sided hypothesis test at alpha of 0.05, we would require a minimum of 11 clusters per arm. With 16 clusters (or HF) over 3 months, we expect a total of 10,500 participants per arm, this sample size is

sufficient to test for non-inferiority in the secondary outcome (clinical cure at day 7) between the control and intervention groups.

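### The quality-of-care survey samples only enrolled children, so its before-after contrast has no common sampling frame and its between-arm round can miss intervention consultations held without the application

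*Protocol*

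**What the plan says.** Protocol section 4.2.2 describes the survey. On facilities: "The surveys will be conducted in a subset (n=18) of randomly selected HFs". On children: "25 consecutive consultations with children enrolled into the study per HF, thus a total of 450 HW/child pairs per round". On timing: "Two main rounds of the survey will be conducted spaced approximately 20 months apart: prior to the intervention and during Phase 2". Three smaller rounds are added "to constitute a third full round of the survey and to systematically compare quality of care between intervention and control facilities". The same sampling rule covers all of them.

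Other sections bear on who counts as enrolled:
- Section 3.1 places the pilot ahead of recruitment. Section 8.1.1 places the first full main-study consent at a child's first Phase 1 visit.
- Section 8.1.1 also states: "A separate consent process will be used for the participants of the mixed-methods operational research studies".
- Section 9.1 allows for up to 30% non-adherence: "Non-adherence here is defined as HWs not using the application for all eligible patients that come to the HF for various reasons".
- Section 9.4 analyses the survey with t-tests and chi-square tests across groups or periods. It has no step for rounds that sample different children.

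**The concern.** Hypothesis 2 (section 2.1) is that ePOCT+ improves quality of care. The survey is meant to show change from baseline and to compare arms. A before-after contrast needs the same kind of child at both ends. If baseline observers must take any sick child, while later observers take only children who were registered and whose caregivers consented to the main study, a change in who is observed is mixed with a change in care.

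The arm comparison carries a different risk. In intervention facilities, registration on the tablet leads into the algorithm; in control facilities it leads only to the end-of-consultation questions (section 8.1.6). A child never entered in the application was therefore seen without the tool in one arm, but had ordinary routine care in the other.

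Tablet data cannot fill this gap for the symptoms and signs that health workers check. The control application records outcome-related data only (Synopsis, Procedures and measurements), and SAP section 5.4 says clinical signs will not be collected systematically. For that indicator, observation is the only source covering both arms.

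**Working it through.** **1. The plan's own figure.** 18 facilities × 25 consultations = 450 per round. This reproduces. No power, alpha or effect size is stated for the survey, so there is nothing further to check on size.

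**2. Can the rule be applied before the intervention?** The Synopsis gives "Phase 1 (data collection): September 2021 – April 2022" and "Phase 2 (data collection): June 2022 – December 2022". The main rounds are about 20 months apart.
- June 2022 minus 20 months = October 2020.
- December 2022 minus 20 months = April 2021.

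The baseline round therefore falls between October 2020 and April 2021. That is 5 to 11 months before the Synopsis start of Phase 1 (September 2021), and 0 to 6 months before the start in section 12.3 (April 2021). Groups 2, 4 and 6 do enrol children before they receive ePOCT+, but only within Phase 1. If the study means the main trial, there is no one to sample at baseline, except possibly at the April 2021 edge.

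**3. How many eligible children could later rounds pass over?** Let *u* be the share of eligible children not enrolled. Eligible consultations behind 450 observed = 450/(1 − *u*).

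| *u* | per facility, 25/(1 − *u*) | per round | passed over |
|---|---|---|---|
| 0 | 25.0 | 450 | 0 |
| 10% | 27.8 | 500 | 50 |
| 20% | 31.3 | 563 | 113 |
| 30% | 35.7 | 643 | 193 |

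**4. What could that do to an estimate?** The mean over all eligible children is (1 − *u*) × enrolled mean + *u* × non-enrolled mean. An enrolled-only estimate is therefore off by *u* × *d*, where *d* is the enrolled minus non-enrolled gap. The documents give no *d*. Assuming gaps of 10, 20 and 40 points:
- *u* = 0: no error.
- *u* = 10%: 1, 2 and 4 points.
- *u* = 20%: 2, 4 and 8 points.
- *u* = 30%: 3, 6 and 12 points.

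For the arm contrast the error is the intervention *u* × *d* minus the control *u* × *d*. Equal registration rates remove it only if *d* is also equal. Non-use of the tool can make *d* larger in the intervention arm.

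**5. Facility draw.** Assume 32 facilities in six groups of 5, 5, 5, 5, 6 and 6 (sum 32) and a simple random draw of 18.
- Chance that some group contributes one facility or none: 44.5%. Chance that some group contributes none: 4.6%.
- Pooled over blocks (16 + 16), chance that an arm has five or fewer facilities: 1.1%; six or fewer: 7.3%.

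**The case against.** Enrolment is not the same as tool use, and this part of the defence stands. Consent is taken at registration, before the consultation (section 8.1.1). SAP section 4.2 keeps every enrolled patient in the intention-to-treat set whether or not ePOCT+ was used, and SAP section 4.1 measures adherence among enrolled children. Enrolled children managed without the tool therefore stay in the survey. Conversely, a child whose caregiver declines may still be managed with ePOCT+ (sections 6.1 and 8.1.1). A reader might infer that the survey is conditioned on tool use; the documents do not support that.

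A reader might also divide by 1 − 0.30 and conclude that the gain is overstated 1.43-fold. That needs 30% of children unregistered, all of them seen without the tool at routine-care level, and every enrolled child managed with it. No document says so. The 30% is a ceiling on application non-use and is not split into unregistered children and registered children seen without the tool. SAP section 3.3 merges it with loss to follow-up. An observer in the room may also reduce non-use.

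The survey has its own consent, so enrolment could mean enrolment in the survey. Section 4.2.2 does not say this, but the reading is possible, and it makes the baseline problem one of wording rather than proof that the round is impossible. The survey timing in Figure 6 is not shown. The timeline table as extracted may be misaligned, so it cannot settle the matter.

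Finally, the arm comparison runs concurrently under one criterion, tablet data cover tests, diagnoses, treatment and referral, and the term random selection does not exclude stratification. These points narrow the concern. They do not supply a baseline rule or bring in the omitted children.

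**Conclusion.** The point holds in limited form. As section 4.2.2 is written, and reading the study as the main trial, the sampling rule cannot be applied to the pre-intervention round, and later rounds leave out eligible children who are not enrolled. The before-after contrast therefore has no common sampling frame.

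The intervention-versus-control round does share a criterion, so it would go too far to say that all tests of Hypothesis 2 compare different populations. Its weakness is narrower: the rule can remove intervention consultations in which the application was never opened, with no counterpart in control facilities.

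The size is unknown. From 0 to about 193 eligible children per round would be passed over if the excluded share lies between 0 and the 30% ceiling. There is no figure for caregiver refusals or for the quality gap, so no bias factor should be quoted. The facility draw is a lesser matter: thin groups are plausible under simple random sampling, but serious imbalance between the pooled arms is unlikely.

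This concerns a stated hypothesis, not the Phase 1 primary or secondary outcome measure.

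**What to change.** - In section 4.2.2, define the frame for every round as consecutive children who meet the age and acute-condition criteria of section 6.1 and whose caregivers give the separate survey consent in section 8.1.1, whether or not they are enrolled in the main study.
- Record main-study enrolment and ePOCT+ use on the observation checklist.
- In section 9.4, report survey results for all observed children and, alongside, for enrolled children only.
- Optionally, draw the 18 facilities at random within group, three from each of the six, so that each block contributes both arms.

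The size is unchanged: 18 × 25 = 450 per round, with the same observers and number of facilities. The cost is a wording change and one checklist item covering both variables. The measured gain in intervention facilities may be smaller, but it would describe all eligible children whose caregivers agree to be observed.
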